- a. higher contrast and spatial resolution of PET/CT for detection of small lesions, which we think will result in improved sensitivity as compared to indium-111 pentetrotide SPECT;
- b. a nearly 75% reduction in the whole body effective radiation dose to patients from a single administration of gallium-68 dotatate (from 16.4 mSv for Octreoscan to 4.3 with Dotatate);
- c. convenience for patients and practical to perform. The entire gallium-68 dotatate PET imaging procedure takes ~2 hours in a single visit, compared to ~24 hours over 2 visits for octreoscan imaging.

II. SPECIFIC AIMS

Aim 1

To investigate if patients with clinically suspected cardiac sarcoidosis exhibit a myocardial OctreoScan or DOTATATE signal high enough (heart-to-blood pool ratio ≥ 2.0) to be visually detected compared to a control group of individuals (expected heart-to-blood pool ratio of ~ 1.0).

Sub-Aim1

To evaluate whether 4-hour (early) compared to 24-hour (delayed) post-OctreoScan injection imaging yields similar lesion detection performance.

Sub-Aim2

To correlate localization and number of increased radiotracer foci between FDG-PET and OctreoScan or between FDG-PET and DOTATATE studies.

Sub-Aim3

To explore the effect of treatment on DOTATATE activity in the heart on follow-up scans

III. SUBJECT SELECTION

We will enroll 30 adult subjects meeting the following inclusion/exclusion criteria.

a. Inclusion Criteria for initial study

- Individuals aged 18 or older

- Documentation of biopsy-proven sarcoidosis OR patients with typical findings on FDG PET and MRI without previous biopsy.

- Clinical suspicion of cardiac involvement defined as the presence of any of the following: high-degree A-V nodal block, complete bundle branch block, reduced left or right ventricular systolic function, any cardiac arrhythmia, and/or unexplained chest pain, dyspnea or syncope

- PET/CT imaging demonstrating abnormal myocardial FDG uptake consistent with active inflammatory myocardium.

b. Exclusion Criteria for initial study

-Initiation of steroids or any other immunosuppressive medication(s) following the completion of FDG-PET, as these medications, in theory, may subsequently suppress OctreoScan or DOTATATE uptake in the heart.

- Patients with history of neuroendocrine tumors (specially insulinomas)
- Patients taking the medication Octreotide
- Patients on total parenteral nutrition (TPN)
- Women who are pregnant or breastfeeding

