Primary Endpoint: Positive or abnormal OctreoScan or DOTATATE uptake in patients with cardiac sarcoidosis

Secondary Endpoint: Differences in OctreoScan uptake at 4 hours vs. 24 hours post-radiotracer injection

c. Statistical methods

Data Ascertainment and Analysis:

All statistical analysis will be done using SPSS (version 21.0). A P value <0.05 will be considered statistically significant for all calculations.

Qualitative assessment of OctreoScan or DOTATATE cardiac uptake: First, Cohen's kappa coefficient will be used to examine the visual inter-rater agreement between readers. We expect a kappa of at least 0.9 (excellent). Subsequently, the percentage of patients with abnormal OctreoScan or DOTATATE will be compared between patients with suspected sarcoidosis and those in a control group (Table 1, Figure 2) using chi2.

Semiquantitative assessment of OctreoScan or DOTATATE cardiac uptake: The heart-to-blood pool ratio is a unitless continuous variable. We will use paired t-test to compare within group OctreoScan uptake between early and delayed imaging, and independent-measures t test to compare OctreoScan or DOTATATE uptake between patients with suspected sarcoidosis and the control group.

We will also investigate whether delayed imaging may lead to improved lesion detection performance due to a higher/better target-to-background ratio compared to early imaging. We will employ chi2 to compare if percentage of patients with abnormal OctreoScan varies significantly both on a patient- and lesion-basis between early and delayed imaging in both study groups.

Evaluation of early vs. delay imaging: We will employ chi2 to compare if percentage of patients with abnormal OctreoScan varies significantly both on a patient- as well as lesion-basis between early and delayed imaging in both study groups.

Comparison with FDG-PET: We will also compare if foci of increased OctreoScan or DOTATATE uptake are similar in number and localization compared to FDG-PET scans.

Expected Results:

Our main hypothesis is that OctreoScan or DOTATATE uptake in the heart will be semiquantitatively (heart-to blood pool ratio will be ≥ 2.0) high enough to allow visualization of OctreoScan or DOTATATE activity in patients with cardiac sarcoidosis, compared to the control group, where myocardial uptake will be similar to blood pool activity (heart-to blood pool ratio of ~ 1.0).

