We also believe that delayed imaging may lead to improved lesion detection performance due to a higher targetto-background ratio compared to early imaging.

Finally, we hypothesized that OctreoScan or DOTATATE will yield a similar number of abnormal cases (on a patient-basis) compared to FDG-PET.

VII. RISKS AND DISCOMFORTS

Radiation Exposure for OctreoScan Protocol:

1. The radiation dose patients will receive in this study is equivalent to an exposure of 16.4 mSv to the whole body (for one OctreoScan injection and two CT scans). This is more than the 3 mSv that the average person in the United States gets each year from natural sources like the sun, outer space, air, food and soil. It is less than the 50 mSv of radiation that is allowed each year for people who are exposed to radiation in their jobs. Although radiation may cause cancers at high doses and high dose rates, currently there are no data to establish unequivocally the occurrence of cancer following exposure to low doses and dose rates – below about 100 mSv. Therefore, the risks of low-level radiation exposure are not known but are thought to be very low.

Radiation risks are reviewed by the Radiation Safety Committee (RSC) at BWH. Subjects who may be pregnant will be excluded from this study, as radiation may cause physical or genetic damage to a fetus. Calculations are below:

Radionuclide	Activity Each	Compound and Method	# Administration	Total Whole-Body Dose
	Administration	of Administration	per Subject	per Administration
Indium-111	222 MBq (6 mCi)	Pentreotide	One	12 mSv^{17}

Type of exam	# Exams per subject	Total Whole-Body Dose per Exam
Low-dose CT for attenuation correction of the chest	Two	2.2 mSv

Total effective dose estimate = 16.4 mSv (total for study)

Radiation Exposure for DOTATATE Protocol:

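### About 20 of 30 patients are imaged with DOTATATE PET/CT but tested against 15 historical OctreoScan SPECT/CT controls, so a small significant difference cannot be attributed to sarcoidosis

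*Combined protocol and SAP*

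**What the plan says.** Biostatistical Analysis, c. Statistical methods, plans two between-group tests. The percentage of patients with an abnormal scan is to be "compared between patients with suspected sarcoidosis and those in a control group (Table 1, Figure 2) using chi2". The heart-to-blood pool ratio is to be analysed by an "independent-measures t test to compare OctreoScan or DOTATATE uptake between patients with suspected sarcoidosis and the control group". The t-test sentence does not itself cite Table 1, but the documents define no other control group. The same section applies p<0.05 to all calculations. Aim 1 asks whether the signal is high enough "to be visually detected compared to a control group of individuals", and Expected Results states the main hypothesis as a ratio of at least 2.0 "compared to the control group, where myocardial uptake will be similar to blood pool activity", that is, about 1.0.

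The rest of the protocol describes the two sides as follows.

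| | Controls (I.c Study Rationale, Table 1, Figure 2) | DOTATATE patients (V.a, V.c, V.d) |
|---|---|---|
| Number | 15 | about 20 of 30 |
| Tracer and modality | OctreoScan SPECT/CT | DOTATATE PET/CT |
| Time after injection | 24 hours | about 60 minutes |
| Centre and period | another centre, 2013, clinical scans | trial centre, prospective |
| Region of interest | about 20 mm, four named walls | 15 mm, at peak activity |

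Section V.a also states that no patient receives both tracers. All 30 subjects must meet the suspected-sarcoidosis criteria, and no control enrolment is described. Statistical methods does not say whether the tracers are tested separately or pooled.

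**The concern.** In the DOTATATE comparison every patient differs from every control in disease status and, at the same time, in tracer, scanner type, uptake time, centre and measurement rule. Nothing in the design separates these: there is no DOTATATE control, no patient scanned with both tracers, and no adjustment. A significant result could come from any of them.

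The protocol sets a standard here that it does not meet for DOTATATE. Study Rationale says that baseline cardiac uptake of these tracers has to be measured systematically before abnormal uptake is studied. That was done for OctreoScan. The only DOTATATE baseline is one illustrative heart in Figure 1, which looked similar to blood pool. Visual similarity does not exclude a shift of 0.1 to 0.2. The Table 1 hearts also looked indistinguishable from blood pool, yet their wall means ran from 0.81 to 1.03, a spread that the protocol attributes mostly to scatter.

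At stake is a reported p value, worded as disease versus control, for two thirds of the sample (20/30 = 67%).

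**Working it through.** The plan gives no sample-size or power figure, so the only figure to reproduce is the control summary.

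**1. Control SD.** The Table 1 wall means are 1.02, 1.03, 0.92 and 0.81, with SDs 0.15, 0.13, 0.15 and 0.15 and n = 15.
- Mean of the four walls: 3.78/4 = 0.945 (stated 0.94).
- SD over 60 wall readings: the within-wall sum of squares is 14 × (3 × 0.15² + 0.13²) = 1.182 and the between-wall sum is 15 × 0.0317 = 0.476. √(1.657/59) = 0.168 (stated 0.17).

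The stated 0.17 is therefore a wall-level SD. The SD of a patient's four-wall mean lies between 0.073 and 0.145, depending on the correlation between walls.

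**2. t test with no disease effect.** Inputs: 20 versus 15, SD 0.17, two-sided 0.05 (sidedness assumed).
- SE = 0.17 × √(1/20 + 1/15) = 0.0581.
- The critical t on 33 df is 2.035, so an observed difference of 2.035 × 0.0581 = 0.118 is already significant.
- For an assumed technical shift d in either direction, the noncentrality is d/SE.

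| Assumed shift | Noncentrality | P(p<0.05), SD 0.17 | SD 0.145 | SD 0.30 (assumed) |
|---|---|---|---|---|
| 0.10 | 1.72 | 39% | 50% | 16% |
| 0.15 | 2.58 | 71% | 84% | 30% |
| 0.20 | 3.44 | 92% | 97.5% | 47% |

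If the tracers are pooled (30 versus 15, shift in the 20 DOTATATE patients only), simulation at SD 0.17 gives 21%, 40% and 60%.

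**3. Chi2.** Study Rationale reports no visual abnormality in the controls, which I read as 0/15 (assumed). Take 5/20 abnormal DOTATATE scans.
- Uncorrected: 35 × (5 × 15)²/(20 × 15 × 5 × 30) = 4.375, p = 0.036.
- Yates: 35 × (75 − 17.5)²/45,000 = 2.57, p = 0.109.
- Fisher: p = 0.057.

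The smallest expected count is 15 × 5/35 = 2.1, and the plan does not say which version applies. Significance needs 5/20 uncorrected, 6/20 with Fisher and 7/20 with Yates. If 10%, 20% or 30% of hearts without disease read abnormal on PET (assumed), these counts are reached in 4%, 37% and 76% of trials uncorrected; 1%, 20% and 58% with Fisher; and 0.2%, 9% and 39% with Yates.

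**4. The effect that the protocol expects.** The hypothesised difference is 2.0 − 0.94 = 1.06. A downward technical shift of 0.20 leaves 0.86. With control SD 0.17 and 20 versus 15, power remains 100% at patient SD 0.17 and about 92% at patient SD 1.0.

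**The case against.** The strongest reply is that the trial does not depend on these tests. The Primary Endpoint is abnormal uptake in patients and, as worded, needs no control group. The main hypothesis is a ratio of at least 2.0 against about 1.0, and step 4 shows that a shift of 0.20 neither creates nor hides an effect of that size. This stands, and it confines the point to the two group tests.

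A second reply is that the tracers are comparable: the protocol says they have similar affinity for the same receptors, and dividing by each patient's own blood pool removes much of the method difference. This stands in part. Affinity says nothing about scanner, timing or region of interest, and the 0.81 to 1.03 spread in Table 1 remained after division by blood pool.

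Third, the documents do not show that any shift exists. A reader might infer an upward shift from the statement on PET, "which we think will result in improved sensitivity as compared to indium-111 pentetrotide SPECT", or a downward one from the expectation that "delayed imaging may lead to improved lesion detection performance due to a higher/better target-to-background ratio compared to early imaging". Neither inference is supported. The first concerns detection of small lesions, and the second concerns OctreoScan at 4 versus 24 hours. Every shift above is an assumption.

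Fourth, centre, period and region-of-interest rule are not specific to DOTATATE. The OctreoScan patients also differ from the controls in centre and period, and they too get regions placed on visible foci. That is correct. What sets the DOTATATE patients apart is tracer, modality and uptake time.

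The FDG-PET comparison does not fill the gap. The hypothesis that "OctreoScan or DOTATATE will yield a similar number of abnormal cases (on a patient-basis) compared to FDG-PET" is tested in patients who were admitted on "PET/CT imaging demonstrating abnormal myocardial FDG uptake consistent with active inflammatory myocardium". At patient level it measures concordance and cannot give specificity.

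**Conclusion.** The point holds for the two between-group tests as they apply to DOTATATE. For about 20 of 30 patients, disease is fully confounded with tracer, modality, uptake time, centre and region-of-interest rule. A p<0.05 driven by a ratio difference of about 0.1 to 0.2, or by about five to seven abnormal reads in 20, cannot be attributed to sarcoidosis. The rates of 39%, 71% and 92% rest on assumed shifts and SD 0.17, and are lower if patients vary more. The chi2 example reaches p<0.05 at 5/20 only without correction.

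A reader might go further and infer that no DOTATATE result, significant or null, can be interpreted. The documents do not support that. A mean ratio near 2.0 would exceed any technical shift considered here, and a mean near 1.0 would fail the protocol's own criterion whatever the controls show. Nor do they support a claim that the peak-activity rule by itself inflates the test by a known amount, because the plan does not say which regional summary enters the t test.

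This should be fixed before analysis. In a pilot it is a matter of which comparisons are tested and how they are described.

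**What to change.** 1. **Separate the tracers.** Analyse and report OctreoScan and DOTATATE separately, and do not pool them against Table 1.
2. **Make the DOTATATE comparison descriptive.** Replace its two significance tests with a side-by-side description. Report the proportion abnormal with an exact CI (for example, 18/20 gives 68% to 99%) and the mean heart-to-blood pool ratio with a 95% CI against the protocol's 2.0. At n = 20 the half-width is 0.19, 0.28 or 0.47 for an assumed SD of 0.4, 0.6 or 1.0. Note that the documents give no derivation of 2.0. Call FDG agreement concordance.
3. **Limit the Table 1 test to the 24-hour OctreoScan images.** Label it a historical cross-centre comparison, and use a regional summary that can be computed the same way in both groups.
4. **Reword Aim 1 and Expected Results.** Apply the control comparison to OctreoScan only, and state that a DOTATATE-versus-normal claim needs DOTATATE normal data.

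The change needs no new patients or scans. It touches Aim 1, Statistical methods and Expected Results, and the region-of-interest wording under Image Interpretation must be aligned with the test.

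The costs are real. Aim 1 loses its control comparison for about two thirds of the sample, and the remaining test rests on about 10 patients against 15. A fixed-wall summary also dilutes focal disease: with one wall at 2.0 and three at 0.945, the four-wall mean is (2.0 + 3 × 0.945)/4 = 1.21, a difference of about 0.26 from 0.945. A highest-wall summary avoids this but needs the controls' patient-level wall values.

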Enrolled patients will be prospectively imaged after injection of either the radiotracer Indium-111 Penteotride (OctreoScan) or DOTATATE. We expect imaging 10 patients with OctreoScan and 20 patients with DOTATATE. No one will receive both radiotracer injections.

Patients will be scheduled for imaging Tuesday through Friday (no Mondays), since the dose of OctreoScan and DOTATATE must be requested by noon for next day delivery. Subjects will be advised to remain well hydrated prior to and for at least one day after tracer injection, this to reduce radiation exposure.

Women may participate in this study only if they are certain they are not pregnant. If the subject is a woman of childbearing age, a pregnancy test will be performed before OctreoScan or DOTATATE injection unless she has a history of total hysterectomy, is post-menopausal for more than 2 years or post-tubal ligation for more than 1 year.

OctreoScan Protocol

Visit 1 (Screening)

- Review the study with the subject and obtain written informed consent and HIPAA authorization.
- Assign the subject a unique study number.
- Record demographics data.
- Record medical history, including a history of biopsy-proven systemic sarcoidosis, diagnosis date, and prior treatments.
- Record concomitant medications.
- Schedule subject for Visit 2.

Visit 2 (Study Day 1)

- Subject arrives to the Nuclear Medicine Department.
- Concomitant medications review.
- Perform abbreviated physical examination.
- Perform and record vital signs.
- Place a peripheral intravenous (IV) line.
- Perform STAT quantitative serum hCG testing prior to each administration of Octreoscan
- Administer OctreoScan IV.
- Observe patient for 30 minutes post OctreoScan injection.
- Patient is to have a break and return to the Nuclear Medicine Department in 4 hours.
- Perform first set of images (~90 minutes)
- Subject can leave the Nuclear Medicine Department

[figure not shown]
Visit 3 (Study Day 2)

- Subject returns to the Nuclear Medicine Department 24 hours after OctreoScan injection
- Record any Adverse Experiences.
- Perform second set of images (~90 minutes).
- Subject has completed the study protocol at this point.

Follow Up

• All patients will be contacted by telephone at approximately 36-48 hours following the last scan for AE monitoring.

Figure 3. Example of Study Visits for OctreoScan Protocol

Study Day 1 (Approximately 6 hours)

Study Day 2 (Approximately 2 hours)

24 hours post	Whole Body	SPECT/CT	

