DOTATATE will be given intravenously at the dose of 4.0 mCi (148 MBq). They will then be observed for 60 minutes post DOTATATE injection at the nuclear medicine lab.

Cardiac acquisition: Individuals will be positioned with the help of a CT topogram (grid over the heart, level of the carina), and a low-dose CT scan (120 kVp, 20 - 30 mA) will be acquired for attenuation correction of PET emission data to cover the entire chest. This will be followed by a 20-minute ECG-gated 3-D PET acquisition of the chest and myocardium.

Imaging Processing:

All PET images will be reconstructed with attenuation correction (Matrix 128x128, OSEM, subsets 28, iteration 2, post filter 6.0 mm), and processed and reviewed using the vendor-supplied HERMES software package.

d. Data to be collected and when the data is to be collected

Visit 1. We will collect demographics data, medical history, prior treatments, and concomitant medications, as well as confirm a negative STAT quantitative serum hCG testing prior to the administration of Octreoscan or DOTATATE.

After visit 3 for OctreoScan or after visit 2 for DOTATATE we will analyze and interpret the images as following:

Image Interpretation for OctreoScan:

OctreoScan uptake in the heart will be assessed both qualitative and semi-quantitatively.

1. Qualitative Assessment of OctreoScan cardiac uptake: Two board-certified nuclear medicine physicians will review the early and delayed whole body planar and SPECT/CT images independently of each other and grade each image set based on OctreoScan uptake in the heart as: 1) negative, 2) borderline positive or 3) definitely positive. In this latter case, the number and location (relative to the left ventricular wall position) of positive lesions will be recorded. Similarly, FDG-PET studies (performed as part of the inclusion criteria) will be reviewed and the number and location of FDG-avid lesions recorded.

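### The visual 4-hour versus 24-hour OctreoScan comparison applies an unpaired chi-square to a two-level cut of a paired, three-level grade

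*Combined protocol and SAP*

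**What the plan says.** Sub-Aim 1 (II, Specific Aims) is "To evaluate whether 4-hour (early) compared to 24-hour (delayed) post-OctreoScan injection imaging yields similar lesion detection performance". Section V.a gives the numbers: "We expect imaging 10 patients with OctreoScan and 20 patients with DOTATATE". Every OctreoScan patient is imaged at 4 hours and again at 24 hours.

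Under Image Interpretation for OctreoScan (V.d), two readers independently grade each early and each delayed image set as "1) negative, 2) borderline positive or 3) definitely positive". For the last grade only, the section adds: "In this latter case, the number and location (relative to the left ventricular wall position) of positive lesions will be recorded".

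Under Biostatistical Analysis, c. Statistical methods, the early versus delayed paragraph reads "We will employ chi2 to compare if percentage of patients with abnormal OctreoScan varies significantly", by patient and by lesion. No analysis of the three grades is planned beyond reader agreement (kappa). The plan does not say whether a borderline scan counts as abnormal. A paired t-test of the heart-to-blood pool ratio between the two times is planned separately. Expected Results states the belief that "delayed imaging may lead to improved lesion detection performance due to a higher" target-to-background ratio.

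**The concern.** Two features of the visual test do not fit the data it will receive.

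First, the chi-square compares two independent groups, but each patient supplies both scans. Its p-value depends only on the two totals, not on how many patients changed or in which direction.

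Second, the grade is cut to two levels before testing. If borderline counts as abnormal, a move from borderline to definite scores as no change. If only definite counts, a move from negative to borderline scores as no change. Switching to McNemar repairs the pairing but still loses those moves.

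With about 10 patients there is little information to spare. A non-significant result could then be taken as support for similar detection, which is how Sub-Aim 1 is worded, although the investigators expect delayed imaging to do better.

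**Working it through.** The plan states no power, effect size or grade distribution for this comparison, so there is no figure of its own to reproduce.

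**Inputs from the document.** n = 10 pairs (V.a); three ordered grades (V.d); significance at 0.05 (Statistical methods). Two-sided testing is assumed.

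**Changes needed by an exact paired test.** If k patients change, all in one direction and by one grade, then p = 2 × (1/2)^k.
- k = 5: 2/32 = 0.0625.
- k = 6: 2/64 = 0.031.

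A paired binary test therefore needs at least six crossings of the cut, all one way.

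**What the cut hides.** Suppose three patients go from negative to borderline, three from borderline to definite, and four do not change.
- Exact paired test on grades: six changes, p = 0.031.
- Exact McNemar at either cut: three crossings, p = 2 × (1/2)^3 = 0.25.
- Planned chi-square: no two counts out of 10 that differ by three reach 0.05. The smallest p is for 0/10 versus 3/10 (equivalently 7/10 versus 10/10): 20 × 30² / (10 × 10 × 3 × 17) = 3.53, p = 0.060.

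**What ignoring the pairing does.** Take 2/10 abnormal early and 7/10 delayed. The chi-square gives p = 0.025 (6/10 delayed would give 0.068). Those totals could come from five gains and no losses (exact McNemar p = 0.0625) or from seven gains and two losses (2 × (1 + 9 + 36)/512 = 0.18). The chi-square cannot tell these apart.

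**Power, under assumptions.** Simulation with n = 10: a normal latent score at each time is cut into three grades, with the early mix, the shift (in SD) and the early-delayed correlation assumed. In rows 1–3, 6 and 7 the mix follows from an assumed ratio distribution. Row 1, for example, has early mean 1.4, SD 0.5 and grade limits 1.3 and 2.0, so negative = Φ(−0.2) = 42% and definite = 1 − Φ(1.2) = 12%. The binary tests are shown with only definite counted as abnormal, the better cut for them in every row.

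| Row | Early negative/borderline/definite, % | Shift, SD | Correlation | Exact paired, 3 grades | Exact McNemar | Planned chi-square |
|---|---|---|---|---|---|---|
| 1 | 42/46/12 | 1.2 | 0.7 | 69% | 15% | 42% |
| 2 | 34/50/16 | 1.0 | 0.7 | 48% | 10% | 28% |
| 3 | 34/50/16 | 1.6 | 0.7 | 89% | 55% | 79% |
| 4 | 40/30/30 | 1.0 | 0.8 | 46% | 14% | 34% |
| 5 | 20/30/50 | 1.0 | 0.5 | 18% | 11% | 30% |
| 6 | 8/42/50 | 0.8 | 0.7 | 9% | 5% | 18% |
| 7 | 16/24/60 | 1.75 | 0.7 | 15% | 13% | 51% |
| 8 | 10/10/80 | 1.0 | 0.8 | <1% | <1% | 6% |

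If borderline also counts as abnormal, McNemar falls to 9%, 3% and 7% in rows 1–3. With no true difference, the exact grade test rejected in about 1% of trials or fewer. The chi-square rejected in about 0–0.3% at correlation 0.8 and at most 1.4% at 0.5.

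**The case against.** **The contrast does not rest on the cut alone.** A paired t-test of the continuous ratio is planned for the same two times, the secondary endpoint is worded as uptake, and Expected Results attributes better detection to a higher ratio. On the latent score of rows 1–3, a paired t-test has 99%, 95% and 100% power. This stands as far as uptake goes. Those figures are an upper guide, because the measured ratio is imperfect. The plan also lists detection as a further question and answers it with chi-square alone. Focus regions are drawn on foci already visible, so a scan without a visible focus has no focus ratio; the four wall regions fill that gap only in part.

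**Detected or not is a legitimate outcome for a detection aim.** Lesions are recorded only for definite scans, so negative to borderline may be a shift in reader confidence rather than a detected lesion. This stands, and it is why the percentages should be kept.

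**The gain can be small, and the chi-square can reject more often.** Rows 5–8 show both. Abnormal FDG uptake is an entry criterion, so many definite early scans are plausible. Nor do the chi-square's extra rejections come from inflated error in these settings, since its null rejection rate is low. What remains is that its p-value does not describe change within patients.

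**Stronger readings to avoid.** A reader might infer that a benefit of delayed imaging would probably be missed altogether, that half of all improvements are lost, or that the grade test always wins by a wide margin. The documents support none of these. The ratio analysis is planned, the share of changes lost depends on an unstated cut and grade mix, and the gain over McNemar is only 2 points in row 7.

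**Conclusion.** The point holds for the patient-level visual comparison. An independent-samples test is planned for paired scans, and it ignores grade changes that do not cross an undefined cut. The 0.031 versus 0.25 example is exact and needs no distributional assumption.

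The size of the power loss rests wholly on assumed grade mixes, shifts and correlations. Against exact McNemar, the grade test gains 54 points in row 1 (69 − 15), 7 in row 5 and 2 in row 7. When most patients are already definite at 4 hours, no exact paired test has useful power (row 8).

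This is a sub-aim in about 10 patients of a pilot study, and it does not affect the primary endpoint. The change is still worth making: the grades are already collected, and a test on them needs no definition of abnormal.

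**What to change.** In Statistical methods, replace the patient-level early versus delayed chi-square with an exact paired test (sign-flip permutation or exact Wilcoxon signed-rank) on each patient's delayed-minus-early grade. Name in advance the single reading used per patient, for example the two-reader consensus.

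Report the 3x3 early-by-delayed table, with the numbers improved, unchanged and worsened. Keep the percentage abnormal at each time, at a cut stated beforehand, with exact McNemar and a confidence interval for the paired difference. State that a non-significant result in about 10 patients will not be read as showing similar detection.

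The cost is a few lines of text and no new data. A grade shift is slightly less simple to report than a difference in percentages. The lesion-level comparison is outside this change.
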